4.3 Handling of Missing dates

Medications with a missing start date, whose stop date is either unknown or after the date of the first dose of study drug, will be considered concomitant. Medications with a missing start date, whose stop date is prior to the date of the first dose of study drug, will be considered as prior medications.

Where the adverse events start dates of year part are missing then the value will not be imputed. For the partial missing situation (month or day missing), the value will be imputed for the analysis purpose.

Missing pattern	Start Date / Pre-Dosing	End Date / Post-Dosing	
completely missing	leave missing		
missing year	leave missing		
missing month	set to 'JAN'	set to 'DEC'	
missing day	set to '01'	set to last day of the month	
missing month and day	set to '01JAN'	set to '31DEC'	
missing time	set to '00:00:00'	set to '23:59:59'	
(concomitant	missing hours: 0	missing hours: 23	
medication)	missing minutes: 0	missing minutes: 59	
	missing seconds: 0	missing seconds: 59	
missing time	set to '23:59:59'		
(adverse event)	missing hours: 23		
	missing minutes: 59		
	missing seconds: 59		

These rules apply to AE and concomitant medication. For AE, beginning/end date of AE, first date of study treatment and date of death are considered to avoid inconsistency.

TP-GDO-WW-016-01 Effective Date: 28Aug13 Related to: SOP-GDO-WW-019

Page 12 of 60

For Visit data other than efficacy, only missing time rules apply. For efficacy visit data, no imputation is made. For birth date, set missing month to '06' and/or set missing day to '15'.

4.4 Study Subjects

4.4.1 Disposition of Subjects

Summary tables of subject disposition will be provided as follows:

- A summary table of the number of subjects who were randomized to study treatment, number of subjects receiving at least one dose of study drug, number of subjects ending the double-blind period, number of withdrawals from the double-blind period, reason for withdrawal in the double-blind period, number of subjects entering the safety follow-up after double-blind period, number of subjects finishing the safety follow-up after double-blind period, number of subjects entering the open-label extension period, number of withdrawals from the extension period, reason for withdrawal in the extension period, number of subjects conducting last observation visit or withdrawal visit will be provided by treatment group and overall for both the double-blind and the open label extension period.
- A by-subject listing of disposition status, including the date of informed consent, date
 of treatment with study drug and study completing/withdrawal, and reason for
 withdrawal from treatment.

4.4.2 Protocol Deviations

Major protocol deviations are defined as those deviations from the protocol likely to have an impact on the subject's rights, safety, well-being, and/or on the validity of the data for analysis. The impact of major protocol deviations on the efficacy results will be investigated by assessing the robustness of the study results and conclusions to the choice of analysis population (ITT vs per-protocol population, see Section 4.5),

A summary table and listing of protocol deviations will be provided as follows:

- The number and percentage of subjects without any major deviation, with at least 1
 major protocol deviation, and type of major protocol deviations will be summarized by
 randomized treatment group, overall and by site. (Analysis population: All
 Randomized Subjects)
- A by-subject listing of major protocol deviations will be presented. (Analysis population: All Randomized Subjects)

4.5 Analysis Populations

The intent-to-treat (ITT) population consists of all randomized subjects and will serve as the primary population for the analysis of efficacy. Subjects will be analyzed as randomized for analysis purposes. In case a patient is incorrectly stratified at time of randomization the analysis will be performed as stratified during randomization.

The Per-Protocol Set population (PPS) will include all patients in the ITT population who

received at least 3 doses of study drug, and without any major protocol deviations which are considered to have an impact on efficacy. Subjects will be analyzed as treated for analysis purposes in the PPS.

The Safety Set (SAF) population will include all randomized subjects who have received at least one dose of active study drug or placebo. Subject will be included in the treatment group corresponding to the trial treatment they actually received for the analysis of safety data using the SAF population, i.e. patients who received at least one dose of SA237 will be assigned to the SA237 treatment arm, irrespective of randomized arm.

The All-Subjects-Treated (All SA237) population will be defined as all enrolled subjects who took at least one dose of active study drug at any time. Date of the first active study drug administration will be defined as Day 1 for All SA237 analysis (i.e. Day 1 of subjects randomized to the placebo group is redefined on the day of first dose of SA237 when entering extension period.

The Pharmacokinetics Per-Protocol Set (PK-PPS) and immunogenicity (anti-SA237 antibody) will include all subjects in the SAF with at least 1 valid post-dose concentration result with a dosing record and sampling time. Pharmacodynamics variables will be analyzed using the SAF population.

The following summary and listing will be provided based on all randomized subjects:

- A summary of analysis populations, including the number and percentage of subjects in the defined analysis sets by treatment group and overall.
- A by-subject listing of analysis population (ITT, PPS, SAF, All SA237 and PK-PPS) information will be provided.

This listing should include: subject number, inclusion/exclusion flag for each population and reason for exclusion from each population.

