If a patient has difficulty visiting the study site within three days, the patient can visit a local clinic/hospital to receive rescue therapy for clinical relapse, and then visit the study site during or immediately after rescue therapy for clinical relapse. Alternatively, the examining Investigator may visit the local clinic/hospital to conduct the EDSS/FSS assessment during rescue therapy for clinical relapse.

If the patient is seen at a clinical facility other than the study site, the patient should show the patient ID card which includes the Investigator's contact information to the treating physicians/nurses at the local clinic/hospital and the study site must make every effort to obtain medical records from the facility, including information on treatment administered and the nature of the symptoms and signs observed.

Assessment of relapse is summarized in [Figure 2](#).

Figure 2 Assessment of Relapse

Each extra visit following relapse will be captured in the electronic case report form (eCRF) and a separate Relapse Assessment Form will be completed by the site and sent (e.g., by fax, e-mail) with the accompanying necessary data, into PAREXEL immediately regardless of the assessment of the site staff about whether potential relapse meets protocol-defined relapse and regardless of the time when EDSS/FSS assessment was performed. During the double-blind period, the form and the data will be reviewed by a CEC. The CEC will be able to request additional information to assist in the determination of a relapse if necessary. The CEC will review all cases of relapse and adjudicate each to see if it meets the protocol definition of a relapse. In order to ensure that no relapse events were missed by the Investigator, the adjudication process will include a concurrent review of all cases for potential relapses that may be missed. The relapse which is regarded as a protocol-defined relapse by the CEC followed by confirmation that the EDSS/FSS assessment was performed within seven days after the patient reported the symptoms to the site, will be treated as an event.

The CEC will be comprised of physicians with expertise in NMO and NMOSD. The committee will be responsible for validating each reported relapse event, in a blinded fashion, to determine the event as to whether it meets the criteria of a protocol-defined relapse. Further details regarding the CEC responsibilities and the process of adjudication are described in the CEC charter.

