4.3.2.1 Satralizumab and Placebo: Double-blind period

The patient will receive an SC injection of satralizumab or placebo at Weeks 0, 2 and 4, and Q4W thereafter during the double-blind period. The double-blind period ends when either the patient has a protocol-defined relapse which is adjudicated by CEC, the total number of registered relapses is 44 or 1.5 years after the date of randomization of the last patient enrolled, whichever comes first.

Patients who experienced a relapse during the double-blind period should continue the double-blind period regardless of rescue therapy unless the patient experiences a relapse which is adjudicated by CEC as a protocol-defined relapse, and will continue administration of study treatment at the discretion of the Investigator.

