4.3.2.2 Satralizumab: Extension period

Patients who complete the double-blind period (see the section “Length of Study” in PROTOCOL SYNOPSIS) or experience a protocol-defined relapse which is adjudicated by the CEC in the double-blind period can enter the open-label extension period. In the open-label extension period, the patient will receive an SC injection of satralizumab at Week 0, 2 and 4, and Q4W thereafter, *with the last study drug administration on or before 31 December 2021.*

For patients who experienced a protocol-defined relapse which is adjudicated by CEC, satralizumab should start in the stable disease condition (Day 31 or later, where Day 1 is defined as the day of onset of a protocol-defined relapse which is adjudicated by CEC). For patients who completed the double-blind period, satralizumab should start after 4 weeks (\pm 7 days) from the last dosing in the double-blind period.

Patients who experience a relapse during the extension period will continue administration of satralizumab at the discretion of the Investigator.

In the OLE period after Week 48, and in accordance with local regulations, administration of satralizumab prefilled syringes outside of the study site (e.g., self-administration or administration by a caregiver after completing training, administration by the patient’s [local] general physician, or home administration by a mobile nurse) will be allowed in emergency situations such as the SARS-CoV-2 (COVID-19) pandemic.

Following the implementation of Protocol Version 10 and in accordance with local regulations, administration of satralizumab prefilled syringes outside of the study site (e.g., self-administration or administration by a caregiver after completing training, or home administration by a mobile nurse) may be allowed on scheduled study drug administration days that do not require additional assessments that must be performed on site ([Appendix 1](#)).

Guidelines for dosage modification and treatment interruption or discontinuation are provided in Section [5.1](#).

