6.1 ANALYSIS POPULATIONS

6.1.1 Efficacy Analysis Populations

The intent-to-treat (ITT) population will serve as the primary population for the analysis of efficacy, which consists of all randomized patients in the study. Patients will be analyzed as randomized for analysis purposes.

The Per-Protocol Set population (PPS) will include all patients in the ITT population who received at least 3 doses of study treatment, and without any major protocol deviations which are considered to have an impact on efficacy. Patients will be analyzed as treated for analysis purposes in the PPS.

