Using the proportion of zero under supposed ARR distribution, we estimate the relapse-free rate at a year in placebo group at 32.3%. The relapse-free rate is assumed to follow the exponential distribution with a constant hazard, and then we set the hazard for 1 year of 1.1295 in placebo group.

According to tocilizumab case report in NMO patients, the pre- and post- baseline relapse counts were reduced from total 4 counts per 6 months to 1 count per 6 months. Then the pre- and post- baseline ratio of 0.25 is used as the estimation of the mean ARR ratio of tocilizumab compared with placebo. Under the assumption of ARR and relapse-free rate distribution above, the mean ARR ratio is coincided with the hazard ratio. The primary rationale for the mechanism of anti-IL-6 blockade in NMO/NMOSD is the expected inhibition of the survival of plasmablast followed by a reduction in anti-AQP4 antibody. Given that the reduction in anti-AQP4 antibody is required for prevention of relapse, and considering the half-life of immunoglobulin G, sufficient effectiveness might not be expected for an initial period of a few months even if IL-6 signaling is inhibited immediately. So we have set the hazard ratio of satralizumab over placebo at 1.0 for an initial 2 months from randomization and at 0.25 after an initial 2 months from randomization.

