4.9 Treatment Compliance

Overall compliance will be assessed for each subject. Compliance will be computed by determining the number of SC injections relative to the number of SC injections that should have been administered. The compliance will only be evaluated during the double-blind period. For subjects who experience a protocol-defined relapse which is confirmed by CEC or discontinued from study treatment early, the number of planned and actual SC injections will be counted based on the visits before the discontinuation. Treatment compliance will be summarized in terms of compliance based on the Safety population.

Compliance will be calculated using the following formula:

Compliance (%) =
$$\frac{\text{Number of SC injections during the double-blind period}}{\text{Number of planned SC injections during the double-blind period}} \times 100$$

The following summaries and listings will be provided:

• A summary table of compliance will be presented by treatment group, and overall. The number and percentage of treatment compliance will also be presented by categorized compliance as: <80%, 80%-100%, >100%.

TP-GDO-WW-016-01 Confidential Version 7.0 Effective Date: 28Aug13 Version Date: 28NOV2018

Related to: SOP-GDO-WW-019

Page 16 of 60

 A by-subject listing of study drug administration as well as overall compliance during study duration of the double blind and study duration of the SA237 exposure

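### The three-dose rule for the per-protocol set can remove fully compliant early relapsers, so comparing ITT with PPS does not isolate the effect of protocol deviations

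*SAP*

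**What the plan says.** SAP 4.5 admits to the PPS those ITT patients who "received at least 3 doses of study drug, and without any major protocol deviations" thought to matter for efficacy. Protocol 6.1.1 has the same rule ("received at least 3 doses of study treatment, and without any major protocol deviations"). Neither text states the period over which doses are counted, and neither makes an exception for a patient who relapses before a third dose is due.

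Doses fall at Weeks 0, 2 and 4, so the third is due on Day 29 (Protocol 4.3.2.1; Appendix 1, Table 6). Under Protocol 4.3.2.1 a relapsing patient stays in the double-blind period "unless the patient experiences a relapse which is adjudicated by CEC as a protocol-defined relapse", and whether injections go on after a relapse is left to the Investigator. The adjudicated protocol-defined relapse is the primary event, and time to first relapse (TFR) runs from randomisation (SAP 4.10.2).

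SAP 4.4.2 gives the PPS its purpose: "The impact of major protocol deviations on the efficacy results will be investigated by assessing the robustness of the study results and conclusions". The comparison it has in mind is ITT against the PPS. For compliance, SAP 4.9 treats the early relapser differently from SAP 4.5: "the number of planned and actual SC injections will be counted based on the visits before the discontinuation".

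**The concern.** PPS membership depends partly on the outcome. Take a patient who receives the Week 0 and Week 2 injections, relapses, and is adjudicated before Week 4, or whose injections the Investigator stops after the relapse. Under SAP 4.9 this patient is 2 of 2, or 100% compliant. Under SAP 4.5 the same patient fails the dose count and is dropped together with the event. Because TFR is still measured from randomisation, removing the earliest events moves the PPS hazard ratio towards a post-Week-4 effect.

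ITT and PPS can then differ in a trial with no deviations at all. The sponsor's planning assumption is a case where they would, because it sets the "hazard ratio of satralizumab over placebo at 1.0 for an initial 2 months from randomization" and at 0.25 afterwards.

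The dose count is also ambiguous. Relapsers may enter the extension, where "In the open-label extension period, the patient will receive an SC injection of satralizumab at Week 0, 2 and 4". If those injections count as study drug, membership depends on treatment given after the event, which is not a deviation criterion either.

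What is at stake is the robustness statement based on ITT versus PPS, not the primary test.

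**Working it through.** **Inputs** (Protocol 6.2, SAP 4.14): placebo hazard 1.1295 per year; hazard ratio 1.0 for two months, then 0.25; 90 patients at 2:1 (60:30); 10% dropout over two years; 33 months' accrual; analysis at 44 events or 1.5 years after the last randomisation, whichever comes first. Assumed here: uniform accrual, exponential dropout, unstratified analysis, and a range of adjudication times.

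**Reproducing the plan's figures.** A Gamma-Poisson count with mean 1.35 and variance/mean √2 has P(0) = (√2)^(−1.35/(√2−1)) = 0.323, and −ln(0.323) gives the stated hazard of 1.1295. Simulated log-rank power (6,000 runs) is 78.4% at 40 events, 81.0% at 42 and 83.8% at 44, so 44 events meet the target of at least 80%.

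**How many patients relapse early.** In the first two months the assumed hazard is equal in both arms, so P(onset before day d) = 1 − exp(−1.1295 × d/365.25):

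- d = 7: 0.021, × 90 = 1.9 patients
- d = 14: 0.042, × 90 = 3.8 patients
- d = 28: 0.083, × 90 = 7.5 patients

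Onset alone does not exclude anyone. The relapse must also be adjudicated, or dosing stopped, before the third dose. With an adjudication time of A days, a relapser is lost if onset falls before day 28 − A. The three cut-offs therefore correspond to adjudication in three weeks, two weeks or no time. Protocol 3.1.4 allows seven days for EDSS/FSS and adds that "The CEC will be able to request additional information to assist in the determination of a relapse if necessary", but gives no turnaround.

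**Effect on the hazard ratio.** 4,000 simulated trials per scenario, with no deviations. Non-relapsed patients with under 28 days of follow-up are also excluded from the PPS (mean 1.6). Medians:

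| Scenario | ITT | PPS, 3 weeks | PPS, 2 weeks | PPS, no delay |
|---|---|---|---|---|
| 1.0 for 2 months, then 0.25 | 0.406 | 0.388 | 0.370 | 0.332 |
| Null | 0.999 | 0.999 | 1.002 | 1.001 |
| Constant 0.25 | 0.249 | 0.249 | 0.250 | 0.250 |
| 0.25 for 2 months, then 0.60 (illustrative) | 0.513 | 0.522 | 0.528 | 0.547 |

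In the first scenario about 1.9, 3.8 or 7.3 of the 44 events are removed. Repeat simulations agree within about 0.01. In that scenario the PPS log-rank test rejects in about 85%, 87% or 90% of trials, against 83–84% for ITT, despite having fewer events. Under the null, rejection stays near 5%. With accrual weighted to later months, 0.41 becomes 0.40, 0.38 or 0.34. With a fixed 38-month cut, 0.391 becomes 0.374, 0.359 or 0.324.

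**Under the corrected criterion** (see the fix) the first scenario gives 0.406, equal to ITT.

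**The case against.** - **The PPS is only supportive.** True. ITT is primary, no PPS test is in the gatekeeping sequence of SAP 4.10.1.4, and type I error is not inflated. This limits the seriousness. It does not make the comparison measure what SAP 4.4.2 says it measures.
- **Adjudication is unlikely to be instant.** Also fair. The process runs from patient report to extra visit, EDSS/FSS, form transmission and committee review. The 0.33 figure is a bound, reached only if dosing stops after every early relapse. At three weeks the shift is 0.41 to 0.39, and at four weeks with continued dosing it is zero. Stopping at the Investigator's discretion can still trigger exclusion however slow the committee is.
- **The shift is small against the precision.** With 44 events at 2:1, SE(log HR) ≈ √(1/(44 × 2/9)) = 0.32. Moving from 0.406 to 0.388 or 0.370 is 0.14 or 0.29 SE, and ITT and PPS gave the same significance result in about 95% or 94% of simulated trials. However, the two estimates come from nearly the same patients, and the shift is systematic rather than sampling error.
- **The exclusions are visible.** SAP 4.5 requires set sizes by arm and a by-subject listing of reasons for exclusion. That shows who left, but no planned analysis separates dose-count exclusions from deviation exclusions.
- **Open-label doses might count.** Then many early relapsers would return to the PPS and the figures above would overstate the loss. That case is not quantified. It is a further reason to define the counting period.
- **The corrected rule also refers to the event.** It keeps short-exposure patients who relapse and drops those who withdraw for other reasons. This stands in principle. At the planned dropout the second group is about 0.4% by Day 28 (1 − exp(−0.0527 × 28/365.25), with 0.0527 = −ln(0.9)/2), under half a patient in 90, and the existing rule already excludes them.

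**Conclusion.** The concern holds. As written, the three-dose rule can exclude fully compliant patients because they had the primary event early, so a gap between ITT and PPS cannot be attributed to deviations. Under the planning assumptions the PPS hazard ratio would be more favourable than ITT by about 0.02 to 0.07, with roughly 2 to 7 events lost. The loss falls to zero if adjudication takes four weeks or more and dosing continues. The size rests on an adjudication time that the documents do not give, on uniform accrual, and on counting double-blind doses only. The direction depends on how the early and later hazard ratios compare, and there is no shift if they are equal. The primary result does not depend on this, but the plan should be corrected so that its robustness check does what SAP 4.4.2 intends.

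**What to change.** Replace the dose criterion in SAP 4.5 and Protocol 6.1.1 with:

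> Received at least three double-blind doses or, if a protocol-defined relapse or the clinical cut-off date occurred before the third scheduled dose, received all double-blind doses scheduled up to that date.

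The deviation criterion stays as it is, and patients who withdraw early for other reasons remain excluded. This settles which period's doses count and brings the PPS into line with the logic of SAP 4.9.

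Protocol 1.3 reports the double-blind period as completed. If its analysis has been done, keep the PPS as defined and report this version beside it, labelled post hoc.

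The cost is one sentence in each document, or one additional supportive analysis. A few patients with fewer than three doses enter the PPS, and its hazard ratio may become slightly less favourable.

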3 INVESTIGATIONAL PLAN

3.1 Overall Study Design and Plan

This is a multicenter randomized, double-blind, placebo-controlled parallel assignment study followed by an open-label extension (OLE) period. Patients will be randomized to two groups (2:1, Group A or B) and will receive subcutaneous (SC) SA237 (Group A) or placebo (Group B) at Weeks 0, 2, 4, and every 4 weeks (Q4W) thereafter. The randomization will be stratified by prior therapy for prevention of NMO/NMOSD attack (B-cell depleting therapy or immunosuppressants/others) and the most recent attack in the last one year prior to screening (first attack or relapse). If a patient was administered B-cell depleting therapies (e.g. anti-CD20 antibody [e.g. rituximab], anti-CD19 antibody) at least once in the year prior to baseline, the patient will be stratified into "B-cell depleting therapy group" and otherwise into the "immunosuppressants/others group" (e.g. oral corticosteroids, azathioprine, mycophenolate mofetil, cyclosporine, methotrexate, tacrolimus).

Patients who experience a protocol-defined relapse which is adjudicated by the Clinical Endpoint Committee (CEC) in the double-blind period or complete the double-blind period can enter the open-label extension period. The double-blind period of the study ends when the total number of CEC-confirmed protocol-defined relapses is 44. At the end of the double-blind period, the clinical cut-off date for the primary analysis will be on the day of the onset of the protocol defined 44th relapse (adjudicated by the CEC) or 1.5 years after the date of randomization of the last patient enrolled, whichever comes first. In the extension period, patients can receive open-label treatment with 120 mg SA237 SC at Weeks 0, 2, 4, and every 4 weeks (Q4W) thereafter, until commercial availability of SA237 or Sponsor's decision to discontinue the development program.

For patients who experience a relapse in the double-blind period, appropriate rescue therapy for relapse will be administered. For patients who experienced a relapse which is adjudicated by the CEC as a protocol-defined relapse, SA237 should start under stable disease conditions (i.e. Day 31 or later, where Day 1 is defined as the day of onset of a protocol-defined relapse confirmed by CEC). For patients who completed the double-blind

TP-GDO-WW-016-01 Confidential Version 7.0 Effective Date: 28Aug13 Version Date: 28NOV2018

[figure not shown]
Related to: SOP-GDO-WW-019 Page 8 of 60

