4.2 General Presentation Considerations

The analyses periods are defined as follows:

- Study duration of double blind period for efficacy analysis
 - Study duration of double-blind period starts on the day of the randomization. The double-blind period ends on the earliest day of 1) clinical cutoff date (CCOD), 2) the day before the first treatment in the extension period, 3) the end of the study, or 4) last contact for patients lost to follow up.
- Double blind period for safety analysis
 - Double blind period starts on the day of first dose of study drug. The double-blind period ends on the same day as the efficacy analysis.
- Study duration of SA237 exposure for safety analysis (for All SA237 analysis)
 - Study duration of SA237 exposure starts on the day of first dose of SA237. Study duration of SA237 exposure ends on the earliest day of 1) CCOD, 2) the end of the study, or 3) last contact for patients lost to follow up.

The definition of summaries by visit is as follows:

- Summaries by visit for double blind period
 - Baseline is defined as the latest data before or on the date prior to first administration with either placebo or SA237. Summarized visits except for baseline are defined as follows. Irregular visits such as unscheduled visit between week X, dose outside the visit window (DOW), extra visit at relapsing, and the end of the study are out of scope. Week X visits are

TP-GDO-WW-016-01 Confidential Version 7.0 Effective Date: 28Aug13 Version Date: 28NOV2018

Related to: SOP-GDO-WW-019

Related to: SOP-GDO-WW-019

directly used for categories of time. In other words, time window is not applied. If there are the same visits data, one representative assessment nearest to the scheduled visit day will be summarized.

- Summaries by visit for All SA237 analysis
 - Baseline is defined as the latest data before or on the date prior to first administration of SA237. Summarized visits except for baseline are defined as follows. Irregular visits such as unscheduled visit between week X, dose outside the visit window (DOW), extra visit at relapsing, and the end of the study are out of scope. Time window is applied as if visit schedules continue in the double-blind period. Middle of each specified day of visit will be used for the range of time window of each visit. One representative assessment nearest to the specified day of visit in time window of each visit will be summarized

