4.11 Safety Evaluation

TP-GDO-WW-016-01 Confidential Version 7.0 Effective Date: 28Aug13 Version Date: 28NOV2018

Related to: SOP-GDO-WW-019

Page 27 of 60

Unless otherwise specified, all safety summaries and analyses will be based upon the SAF as defined in Section 4.5

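### SAP 4.5 sets the safety treatment arm by any SA237 dose and names no period; taken literally, it moves placebo relapsers already dosed in the extension into the SA237 column

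*SAP*

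**What the plan says.** SAP 4.5 places each SAF patient in the group for the treatment actually received "for the analysis of safety data using the SAF population" and spells this out as an operational rule: "patients who received at least one dose of SA237 will be assigned to the SA237 treatment arm, irrespective of randomized arm". The sentence contains no period. SAP 4.11 sends the safety output to that definition: unless otherwise specified, "all safety summaries and analyses will be based upon the SAF as defined in Section 4.5". Protocol 6.1.3 says only that SAF patients are analysed as treated, which does not settle the matter.

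The next paragraph of SAP 4.5 defines a separate All SA237 population as "all enrolled subjects who took at least one dose of active study drug at any time", and for that analysis resets Day 1 for placebo patients to their first extension dose.

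SAP 4.2 ends a patient's double-blind period at the earliest of several dates, one of which is "the day before the first treatment in the extension period". For safety, "The double-blind period ends on the same day as the efficacy analysis". SAP 3.1 lets patients with a confirmed relapse enter the extension, where "SA237 should start under stable disease conditions (i.e. Day 31 or later" after onset.

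**The concern.** In a trial without crossover, an at-least-one-dose rule would catch only dosing errors. Here, placebo relapsers can receive SA237 while the double-blind period is still running for other patients. At the cut-off, such a patient has received at least one dose of SA237 and satisfies the rule as written.

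SAP 4.2 does not prevent this. It limits which events and patient-years count, not the column in which they count. The two rules together mean that a relabelled patient brings only placebo-period data to the SA237 column. The remaining placebo column is then selected on outcome, because only relapsers can leave it by this route. At stake is the by-arm safety comparison at the primary analysis. ITT efficacy is untouched, and patients who complete the double-blind period start the extension after the cut-off.

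**Working it through.** **1. Tracing one patient.** A placebo patient relapses, the relapse is confirmed, and open-label SA237 starts on Day 31 after onset, before the cut-off.
- SAF membership (4.5): yes, through the placebo doses.
- SAF arm (4.5, literal): SA237, through the extension dose.
- Data counted (4.2): first dose to the day before the first extension dose, all on placebo.
- Result: placebo data under SA237.

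If the arm is set by double-blind treatment instead, the label is placebo and nothing moves.

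**2. How many patients.** The plan states no figure to reproduce. Inputs from SAP 4.14 and 3.1: 90 patients randomised 2:1 (60 SA237, 30 placebo); accrual over 33 months; placebo hazard 1.1295 per year; hazard ratio 1.0 for 2 months, then 0.25; 10% dropout over 2 years; cut-off at the 44th event or 1.5 years after the last randomisation, whichever is first. Assumptions added here: exponential dropout, accrual either uniform or rising, and first extension dose between Day 31 and Day 91 after onset. Means over 6,000 simulated trials per accrual pattern (uniform / rising):
- placebo relapsers by the cut-off: 20.8 / 21.0
- placebo non-relapsers: 8.6 / 9.0
- placebo relapsers reaching Day 31 before the cut-off: 19.6 / 19.7 (5th to 95th percentile 16 to 24)
- reaching Day 61: 18.8 / 18.8
- reaching Day 91: 18.0 / 17.9

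Relabelled = uptake × relapsers reaching the start day. Relapsers left on placebo = relapsers − relabelled. For example, at 50% uptake, Day 31, uniform accrual: 20.8 − 0.5 × 19.6 = 11.0 relapsers left beside 8.6 non-relapsers, and 11.0 / 19.6 = 56%.

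| Uptake before cut-off | Relabelled, of about 30 | Relapsers among remaining placebo | Placebo-only patients in SA237 column |
|---|---|---|---|
| 0% | 0 | 70–71% | 0% |
| 50% | 9–10 | 55–58% | 13–14% |
| 75% | 13–15 | 41–46% | 18–20% |
| 100% | 18–20 | 12–26% | 23–25% |

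The last column is relabelled / (60 + relabelled), e.g. 19.6 / 79.6 = 25%. Non-relapsers become the majority of the placebo column once uptake exceeds (relapsers − non-relapsers) / relapsers reaching the start day: (21.0 − 9.0) / 19.7 = 0.61 at the lowest and (20.8 − 8.6) / 18.0 = 0.68 at the highest.

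**3. Patient-years in the 4.2 window, full uptake, Day 31 start.** Placebo 20.0 / 20.2, of which 12.1 / 11.3 would be relabelled; SA237 58.1 / 56.4.

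**4. Direction.** This applies only to output per patient-year, which the SAP plans for serious infections (4.11.7). The rates below are assumed, using the uniform-accrual figures.
- Same event rate in all placebo patients, true rate ratio 2: the table would show (2 × 58.1 + 12.1) / (58.1 + 12.1) = 128.3 / 70.2 = 1.83. This is dilution.
- Relabelled relapsers with twice the rate of the other placebo patients, and no true difference between arms: the placebo average is (7.9 × 1 + 12.1 × 2) / 20.0 = 1.605, and SA237 has the same rate. The table would show (58.1 × 1.605 + 12.1 × 2) / 70.2 = 1.67 against a remaining placebo rate of 1. This is inflation.

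The sign therefore depends on whether relapsers' event rates differ from those of other patients, which the documents do not say.

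**The case against.** The strongest reply is that the context already settles the reading. The authors wrote that a dose at any time counts when they defined All SA237, and left this out of the SAF sentence. If extension doses also set the SAF arm, the SA237 column would hold largely the same patients as All SA237, and the second population would add little. The reference to the randomised arm reads naturally as a rule for dosing errors. By-arm safety output is repeatedly tied to the double-blind period: compliance ("The compliance will only be evaluated during the double-blind period"), serious-infection rates (4.11.7), laboratory shifts (4.11.10), ECG values (4.11.12) and abnormal vital signs (4.11.13). ECG output is also listed for the SAF and All SA237 as two sets. Within the 4.2 window a placebo relapser received only placebo.

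This stands as evidence of intent, and it is why the point is minor. It does not supply the missing rule. SAP 4.5 deals with crossover explicitly for All SA237 and not for the SAF, and no other sentence sets the SAF label.

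Two further objections are accepted. Dilution of adverse event differences does not follow in general. The per-patient-year illustration also does not carry over to the main adverse event tables, which 4.11.3 plans as numbers and percentages of subjects.

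**Conclusion.** The literal rule is wrong as written, and its severity is minor. Under the planning assumptions it would relabel from 0 to about 18–20 of about 30 placebo patients, depending on an uptake that the documents do not give, and about 11–12 of about 20 placebo patient-years at full uptake with a Day 31 start. If the rule is programmed as probably intended, nothing changes.

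A reader might infer more, and the documents do not support it:
- That the safety tables were produced this way: the plan cannot show this, and its context points to the benign reading.
- That adverse event differences would be diluted: this needs constant rates shared by relapsers and non-relapsers.
- That the placebo column would consist mostly of non-relapsers: this needs uptake above 61–68%.
- That pharmacodynamic results are affected: the rule is confined to safety data.

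**What to change.** In SAP 4.5, limit the at-least-one-dose rule by adding *during the double-blind period (Section 4.2)* directly after the reference to the SA237 dose, and end the sentence with *extension-period doses do not change the SAF treatment group and are covered by the All SA237 population*. A cross-reference to the 4.2 double-blind safety period in 4.11.2 and 4.11.3 is optional, since 4.2 already defines it.

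The cost is one phrase and one clause. No new data are needed, and the sample size and efficacy analyses do not change.
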